**Phone Coaching for Weight Loss Maintenance**

**Statistical Analysis Plan**

**NCT04293055**

**Last Updated: 6/6/2024**

**Statistical Plan.** Descriptive statistics will be used to compare the coaching and the control groups. Only individuals who regained 1.5% of their weight and triggered randomization will be included in the subsequent analysis, given the focus of the study is to compare conditions for individuals who experience weight regain. For the primary outcome (e.g., change in percent weight from baseline to 12 months), linear regressions predicting change in percent weight from baseline to 12 months controlling for baseline weight will be utilized. For the secondary outcome (e.g., percent weight change during the 40-day coaching window), linear regressions predicting change in percent weight from trigger day to 40 days post-trigger day controlling for trigger-day weight. Multiple imputation will be used to handle missing data.

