Phone Coaching for Weight Loss Maintenance

NCT04293055

Last Updated: 10/28/2020

Weight Maintenance Rescue Study

Participants from previous studies at the Weight Control and Diabetes Research Center who have completed a 1-year weight loss (WL) program and lost $\geq 5\%$ of their initial body weight will be eligible to participate in this WL maintenance study (eligible age range: 18-72 years). While attending their 1-year assessment visit, eligible participants will be provided with information about our WL maintenance study and asked whether they would be interested in participating. They will have the opportunity to discuss this study with a member of the research team and if interested, they will sign the informed consent document. For those individuals unable to attend an in-person visit, they will be mailed two informed consent documents and a member of the research staff will review the consent document and all study procedures with him/her via the phone. Further, this individual will have the opportunity to ask questions related to the study prior to signing the informed consent document. Once signed, the participant will mail one of the signed consent documents back to the researchers using a postage-paid envelope. Details for this study are provided below.

Purpose: This WL maintenance study is designed to examine whether the provision of a brief period of phone coaching to individuals who regain $\geq 1.5\%$ from the start of the maintenance study, prevents further weight regain, compared to individuals who do not receive any coaching.

Design: Participants who lost $\geq 5\%$ of their initial body weight after completing a 1-year WL program will have the opportunity to enroll in this WL maintenance study. Those signing informed consent will be randomized at baseline (start of maintenance study) to one of 2 conditions: 1) provision of a brief period of phone coaching as soon as they regain $\geq 1.5\%$ of their starting maintenance weight (Small Regain), or 2) no phone coaching, independent of weight regain (Control). Participants will not be informed of the criteria used to determine who receives phone coaching. Participants will be followed for 1 year and will complete assessments of weight, physical activity and various questionnaires at baseline, 6 and 12 months. They will be compensated \$25 in cash for completion of the 6 and 12 month assessments.

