WL maintenance program components: All participants will be encouraged to continue to weigh themselves daily and they will be provided with a smart scale, which electronically transmits their weight data via cellular network technology so that it can be reviewed weekly by a member of the research team. If the participant is unable to come to our center to pick up a scale, we will mail the scale to his/her house. All smart scales will be programmed with participant's ID number and no personal identifiers will be utilized. If participant's do not weigh themselves for 7 consecutive days, a member of the research staff will contact the participant and encourage him/her to step on the scale. As part of the study, participants will also be provided with a monthly newsletter which will provide them with helpful strategies for maintaining their weight loss long-term. Smart scales will be returned to research staff at the 12 month assessment visit.

Phone coaching intervention: Participants randomized to the Small Regain group will be contacted by a coach if they regain $\geq 1.5\%$ of their starting maintenance weight. To ensure that this is true weight regain and not just a fluctuation of weight on the scale, the participant's weight will need to be above the predetermined threshold for 4 consecutive days or if their 7-day average falls above this threshold (whichever occurs first). The coach will serve as a source of support for the participant after a period of weight regain. The coach will seek to establish rapport and encourage the participant while offering a supportive environment to problem solve around barriers to continued weight loss and set goals related getting back on track, which is consistent with the Supportive Accountability Model by Mohr and colleagues. Participants will

also be encouraged to 'go back to the basics' which include meal planning, self-monitoring, and goal setting. While the structure of the coaching calls will be similar across participants, the content will be tailored to the individual. Coaches will set goals with participants on each call and will follow up with them the following week. Calls will be provided for 4 consecutive weeks. The first call will be approximately 20-30 minutes in duration and follow-up calls will be 10-15 minutes. All coaching calls will be recorded for fidelity purposes.

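### Does the primary regression need day of trigger as a covariate, given that time left after the trigger can range from 361 days to none?

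*SAP*

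**What the plan says.** The SAP, Statistical Plan, first sets the analysis population: "Only individuals who regained 1.5% of their weight and triggered randomization will be included in the subsequent analysis". For the primary outcome it specifies "linear regressions predicting change in percent weight from baseline to 12 months controlling for baseline weight will be utilized". For the secondary outcome it specifies "linear regressions predicting change in percent weight from trigger day to 40 days post-trigger day controlling for trigger-day weight". Trigger day is not a covariate in either model, and no model starts at the trigger and ends at month 12.

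The Protocol, Design, fixes the observation period: "Participants will be followed for 1 year". The Protocol, Phone coaching intervention, confirms regain by a rule on daily scale readings: "weight will need to be above the predetermined threshold for 4 consecutive days or if their 7-day average falls above this threshold", whichever is met first. The Protocol, Purpose, asks whether coaching "prevents further weight regain, compared to individuals who do not receive any coaching".

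**The concern.** A participant who triggers in the first week has almost a year in which to regain further or to benefit from coaching. One who triggers in the last week has almost none. Both enter the same 12-month regression with equal weight and adjustment for baseline weight only. Early triggering may also mark fast regain, so trigger day could predict the outcome, and the secondary analysis already needs it for every participant. Omitting it could waste precision.

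The purpose concerns regain after the trigger, but the primary interval mixes time before and after it, and the one trigger-anchored analysis stops at 40 days. If the main question went unmeasured, or were measured with avoidable noise, the trial could miss a real effect.

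**Working it through.** **1. Range of time after the trigger.** Taking a 365-day year with weighing every day from day 1:
- earliest trigger under the 4-day rule: day 4, leaving 365 - 4 = 361 days
- earliest under the 7-day average alone: day 7, leaving 365 - 7 = 358 days
- latest: day 365, leaving 0 days

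The range is possible. The documents state no sample size, SD or distribution of trigger days, so everything numerical below, apart from identities, rests on assumed inputs.

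**2. Bias.** Coaching starts only after the trigger. Before it, all participants get the same scales, weighing prompts and newsletters (Protocol, WL maintenance program components), and the coaching criteria are not disclosed (Protocol, Design). Trigger day should therefore have the same distribution in both arms, provided it is derived identically in each.

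A simulation checked this with 60 or 100 triggered participants in total, post-trigger drift of 2 to 8 points per year, SD 4 to 6, uniform or early-skewed trigger days, and 1,500 replicates per scenario.
- Constant true effect of -2.0: unadjusted means -1.95 to -2.04 (Monte Carlo SE 0.02 to 0.04).
- Effect proportional to time remaining, true averages -1.00 and -1.51: estimated as -0.98 to -1.00 and -1.51 to -1.52.

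The unadjusted model recovers the average effect even when the effect depends on time remaining.

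**3. Precision.** If trigger day explains a share R² of the outcome variance, the large-sample cut in standard error is 1 - √(1 - R²). In a second simulation, percent change is a personal slope (mean m, SD s at day 365) plus a daily random walk (SD w at day 365). Scale noise has SD 0.8 unless stated, visit error has SD 0.5, and there are 20,000 people per scenario.

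| m, s, w | R² | SE cut |
|---|---|---|
| 0, 2, 5 | 0.000 | 0.0% |
| 3, 2, 5 | 0.021 | 1.1% |
| 3, 5, 3, correlated noise, SD 1.2 | 0.029 | 1.5% |
| 3, 5, 5 | 0.032 | 1.6% |
| 3, 5, 3, correlated noise | 0.060 | 3.0% |
| 1, 5, 3 | 0.064 | 3.3% |
| 3, 3, 3 | 0.081 | 4.1% |
| 3, 5, 3 | 0.110 | 5.7% |
| 5, 5, 3 | 0.152 | 7.9% |
| 3, 3, 1 | 0.402 | 22.7% |
| 3, 5, 1 | 0.446 | 25.6% |

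The two large gains need w = 1, that is, very steady individual regain, which nothing in the documents supports. In finite samples (six of these scenarios) the variance ratio, adjusted to unadjusted, at 50 per arm is 0.913, 0.948, 0.550, 0.601, 0.992 and 1.013. The highest value is 1.040, at 20 per arm. In the simulation of step 2 the SE ratio, unadjusted to adjusted, is 0.99 to 1.16.

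**4. Chance imbalance.** At 50 per arm, a 1-SD chance difference in mean trigger day of 14.2 days, with the steepest slope of 1.00 point per 30 days, shifts the unadjusted estimate by 14.2/30 × 1.00 = 0.47 point. This is not an extra error. A 1-SD imbalance always shifts the estimate by √R² times its own unadjusted SE. With R² = 0.446 for this case, √0.446 = 0.67, so the SE is about 0.47/0.67 = 0.7 point. The shift is already inside that SE and the confidence interval.

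**5. Trigger to month 12.** Measured as a percentage of baseline weight, change from baseline to month 12 = change from baseline to trigger + change from trigger to month 12. The first term is near +1.5% for everyone who triggers (simulated SD 0.26 to 0.72, against outcome SD 2.4 to 6.1) and cancels between arms on average. In the simulation of step 2 the mean arm contrasts for the two outcomes differ by at most about 0.004 point.

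**6. How unequal the times are likely to be.** In the simulation of step 3 only 4.7-17.9% of triggers fall after day 182 and 0.34-1.43% in the last 28 days. The 361-to-0 range describes the extremes.

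**The case for a change.** The best case for adjusting is that it is cheap. The scales record the data, the secondary analysis needs the trigger date anyway, and a prognostic covariate is worth having: at R² = 0.10 or 0.20 the unadjusted model needs 1/(1 - 0.10) = 1.11 or 1/(1 - 0.20) = 1.25 times as many participants for the same precision. A trigger-anchored 12-month analysis would also describe the post-trigger course directly. Late triggers are real too: after day 365 - 28 = 337 the four weeks of calls cannot finish before month 12, and after day 365 - 40 = 325 the secondary window cannot close.

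What stands is that adjustment would be a defensible option. It does not follow that its absence is a fault:
- The gain cannot be shown from the documents and may be nil or slightly negative.
- If randomization is at baseline, as the Protocol, Design, says, trigger day arises after randomization, and the confirmation rule is written out only for the Small Regain group. Adjusting then assumes that assignment does not affect when people trigger, beyond the SAP's existing assumption that it does not affect who triggers.
- A main effect of trigger day still gives one estimate averaged over unequal remaining time. Only an interaction or subgroup analysis would show whether the effect varies with time left.

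Two neighbouring matters are separate from this point and are not settled by it: the Protocol randomizes at baseline while the SAP speaks of a trigger for randomization, and the SAP does not list the variables in the imputation model. If dropout depended on both arm and trigger day, the second could matter; the no-bias result above is for complete data.

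**Conclusion.** The concern does not hold. The SAP's primary model is a valid analysis of 12-month change among triggered participants, and its contrast captures regain after the trigger. Omitting trigger day causes no bias. The likely loss of precision is small: an SE cut forgone of 0-8% in nine of 11 assumed scenarios, 23-26% only where individual regain is very steady, and a possible variance cost of up to 4% from adjusting at 20 per arm.

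This rests on three conditions: the trigger is derived the same way in both arms, assignment does not affect who triggers before coaching begins, and the data are complete or adequately imputed. The sizes rest on assumed drift, variability and trigger-day distributions, because the documents give none.

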Data collection and management. All assessment data will be entered into the data management program by a member of the research staff. Range checks will be built into the data entry procedure to alert staff to data that requires additional clarification. [name] will conduct error checking and preliminary analyses of all data to ensure accuracy. Questionnaire data will be collected using REDCap (Research Electronic Data Capture), which is a secure, web-based application designed to support data capture for research studies and is hosted by Lifespan. It provides an intuitive interface for validated data entry, audit trails for tracking data manipulation and export procedures, and automated export procedures for seamless data downloads to common statistical packages. Only IRB approved research staff will have access to the REDCap platform and staff members will be granted access through a secure login provided by the study PI.

PROTECTION OF HUMAN SUBJECTS

Risks to Subjects

Human Subject Involvement and Characteristics: Participants in this study will be a sample of men and women, aged 18-72 years, who recently completed a 1-year weight loss program and achieved a weight loss $\geq 5\%$ of initial body weight. Further, they cannot currently be enrolled in another weight management program at the time of study entry.

Sources of Research Material: Data will be obtained specifically for research purposes via direct measurement and questionnaires. Height and weight will be directly measured, physical activity will be objectively-assessed using the Actigraph GT9X Link accelerometer, and demographic information, and dietary and weight control practices will be assessed via questionnaire. Daily weights will be collected via Smart Scales, ever time the participant weighs him/herself. Further, intervention adherence data, the number of phone coaching calls completed, the length of each phone call, and interventionist time will recorded.

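### Secondary model: trigger-day weight says almost nothing about how far the person was above their own starting weight, so some precision is given away; a one-term fix, with no bias at issue

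*SAP*

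**What the plan says.** The SAP's Statistical Plan specifies, for the secondary outcome, linear regressions for "change in percent weight from trigger day to 40 days post-trigger day controlling for trigger-day weight". It names no other covariate. It does not give the unit of trigger-day weight, and it does not say whether the trigger-day or day-40 value is one reading or an average. The primary model is parallel, with change from baseline to 12 months "controlling for baseline weight will be utilized". The analysis set is restricted: "Only individuals who regained 1.5% of their weight and triggered randomization will be included in the subsequent analysis". Missing data are to be multiply imputed, with no list of variables.

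In the protocol (Design; Phone coaching intervention) the trigger is a regain of at least 1.5% relative to each person's own weight at the start of maintenance. It is confirmed by four consecutive days over the threshold or a 7-day average over it, whichever comes first. The stated reason is "To ensure that this is true weight regain and not just a fluctuation of weight on the scale". Under Sources of Research Material: "Daily weights will be collected via Smart Scales".

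**The concern.** The outcome starts from a scale reading taken just when a run of readings has crossed a threshold. Part of that reading is day-to-day noise, and the noise enters the change score with the opposite sign: a reading that is high by chance is followed, on average, by a larger fall. A covariate can absorb this only if it shows how far the reading lay above the person's own reference. Absolute weight cannot, because people differ in body size by far more than they fluctuate. The primary model includes baseline weight; the secondary model does not, so it cannot reconstruct how much each person had regained. At stake is the width of the confidence interval for the 40-day coaching effect.

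**Working it through.** **No stated figure to reproduce.** The documents give no sample size, power, effect size or SD. Every size below rests on assumed inputs.

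**Step 1: unit of the covariate.** As a percent of baseline, the primary model's baseline weight would be 100 for everyone and could not serve as a covariate. It must be absolute weight, and trigger-day weight is most naturally read the same way.

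**Step 2: mechanism.** Write the observed percent excess at trigger as x = τ + e, with τ the true excess and e the scale noise (noise in the starting weight also enters x). The 40-day change is approximately (τ40 + e40) − (τ + e). It contains −e while x contains +e, so the slope of change on x is negative without any coaching.

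**Step 3: information in absolute weight.** Assume mean weight 92 kg, between-person SD (SDw) of 12 to 25 kg, and SD of percent excess (SDx) of 0.3 to 0.85 points, the last being roughly the spread seen in the simulations of step 4. Then

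r = 0.92·SDx / √(SDw² + (0.92·SDx)²).

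- SDx 0.3, SDw 25: 0.276 / 25.0 = 0.011, R² about 0.01%.
- SDx 0.5, SDw 18: 0.46 / 18.0 = 0.026, R² about 0.07%.
- SDx 0.85, SDw 12: 0.782 / 12.03 = 0.065, R² about 0.42%.

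**Step 4: simulation under the protocol's trigger rule.** Further assumptions: daily noise SD 0.4 to 1.0% with lag-1 autocorrelation 0 to 0.5, daily random-walk SD 0.05 to 0.2%, mean annual regain 3% (SD 4%), and starting weight measured with the same noise. The SAP's model was compared with the same model plus x.

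- Adjusting for trigger-day weight left the residual SD equal to the unadjusted one, to two decimals, in every scenario.
- The slope on x was −0.46 to −0.90.

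| Case | Residual SD, SAP model | Residual SD with x | Variance reduction | SE reduction |
|---|---|---|---|---|
| Quiet end | 1.41 | 1.40 | 1 − (1.40/1.41)² = 1.4% | 0.7% |
| Middle | 1.05 | 0.98 | 1 − (0.98/1.05)² = 13% | 7% |
| Noisy end | 1.40 | 1.19 | 1 − (1.19/1.40)² = 28% | 15% |

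The middle case has noise 0.6%, random walk 0.1% per day and no autocorrelation. Entering starting weight beside trigger-day weight, in place of x, gave the same residual SD of 0.98.

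A second set of 36 scenarios (noise 0.5 to 1.0%, autocorrelation 0.2 to 0.5, 50 to 90% of days weighed) gave variance reductions of 0.8 to 17.2% and SE reductions of 0.4 to 9.0%. The typical variance reduction was 7%, that is 1 − √0.93 = 3.6% of the SE. With both weights taken as 7-day means, the gain fell to 0 to 1% of variance.

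**Step 5: what it buys.** For an assumed 0.5-point effect, two-sided 5% and 80% power, n per arm = 2(1.96 + 0.84)²·SD² / 0.5². The SAP model against the model with x needs 125 against 124 (quiet), 70 against 61 (middle) and 124 against 89 (noisy). At an assumed 40 per arm, middle-case power is 57% against 63%.

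**Step 6: bias.** Across 4,000 simulated middle-case trials of 40 per arm, with one trigger rule for both arms and a true effect of −0.50, the mean estimates were −0.500 (SAP model) and −0.497 (with x). Their empirical SDs were 0.233 and 0.215.

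**The case against.** The SAP follows a common convention: each change score is adjusted for its own starting value. A more prognostic covariate improves efficiency but corrects no error. The typical gain is small, every size is assumed, and the two simulation sets differ about twofold in their typical variance gain. The trigger rule exists to screen out fluctuation, and on the 7-day path the trigger-day reading need not itself be over the threshold. All of this stands, and it is why the point is minor.

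Two of the SAP's silences also matter. If trigger-day weight were expressed as a percent of starting weight, it would already be the proposed covariate and the point would fall away. If both weights were 7-day means, almost nothing would be gained. Absolute, single-day weight is the natural reading, but it is an inference.

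Stronger readings are tempting and are not supported:

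- **Regression to the mean biases the coaching effect.** A reader might infer this from the selection on high readings. The average fall is shared by both arms and goes into the intercept; step 6 shows no bias. This does assume one trigger rule for both arms, and the protocol spells the rule out only for Small Regain.
- **Chance imbalance in trigger readings is a second harm.** With an SD of x of 0.66 and 40 per arm, a typical imbalance is 0.66 × √(2/40) = 0.15 points; at slopes of −0.3 to −0.8 it moves the estimate by about 0.05 to 0.12. That is ordinary random error already inside the SAP model's SE (0.22 to 0.54 for residual SDs of 1.0 to 2.4). It is the same precision loss described again.

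One might also object that x is measured after randomization, if randomization is at baseline as the protocol's Design section has it. So is the SAP's own covariate, on the same day. Both precede coaching, and x adds no new kind of conditioning.

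**Conclusion.** The point holds as a modest loss of precision in the secondary analysis. That the planned covariate is nearly inert is the firmest result: it holds across the whole assumed range of body-weight SDs. The size of the loss is much less certain: roughly 1 to 28% of residual variance, or an SE about 0.4 to 15% larger than it need be, commonly 3 to 8%. This rests on assumed noise and drift, on absolute single-day weights, and on one trigger rule in both arms. When true drift dominates scale noise the loss is negligible. The primary outcome is not affected.

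**What to change.** In the secondary regression, keep trigger-day weight and add percent above starting maintenance weight on trigger day:

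100 × (trigger-day weight − starting weight) / starting weight.

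Entering starting weight beside trigger-day weight is practically equivalent; use one form or the other. Put the same term in the imputation model, so that imputed day-40 values keep its relation with the outcome. In the same edit, state the unit of trigger-day weight and whether the trigger-day and day-40 values are single readings or averages.

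The cost is one degree of freedom and a line of SAP text. No new data are needed, since applying the trigger already requires both weights.
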